### 4.2 Study Population

Subjects who have ESRD and are currently receiving maintenance hemodialysis via a tunneled, cuffed hemodialysis catheter ("Subjects") will be enrolled in a prospective, nonrandomized, multicenter, open label clinical study designed to evaluate the safety and effectiveness of the Amplifi System as specified in this protocol ("Protocol").

### 4.3 Study Design

The Study is a prospective, nonrandomized, single-arm, open-label clinical study evaluating the use of the Amplifi System.

**Up to ten (10) Subjects** with a forearm or upper arm cephalic vein with a diameter  $\geq 1.7$  mm and  $\leq 3.2$  mm, and radial artery diameter  $\geq 2.0$  mm who have ESRD and are receiving maintenance hemodialysis using a catheter for vascular access. The Subjects will be treated in an inpatient (hospital) setting and will receive Amplifi System treatment and undergo subsequent AVF creation (a "Study AVF") immediately after treatment. Amplifi System removal

## Clinical Protocol FIH-3

Doc No: CLINP1837  
Revision: D  
DCO No: 25-009  
Effective Date: 02/06/25

immediately followed by AVF creation will be performed when Subject had:

- Amplifi treatment for  $\geq$  48 hours duration and physician determined that cephalic vein is suitable for AVF creation determined by physician (e.g., vein diameter  $\geq$  3.3 mm as defined in Dageforde as Quartile 3 and baseline diameter increased  $\geq$  50%); or
- Amplifi treatment could be extended up to 60 hours ( $\pm$  12hrs) if the cephalic vein was not determined to be adequate by the investigator.

After the Amplifi System treatment period, the device will be removed completely and an AVF will be made using the treated cephalic vein. After AVF creation, Subjects will be discharged from the hospital with outpatient follow up visits 1, 2 and 6-weeks after AVF creation.

### 4.4 Study Site and EC / EC

Subjects will be enrolled at Sanatorio Italiano, Asuncion, Paraguay Investigation Site.

### 4.5 Primary Clinical Measures

#### Effectiveness Measures

- **Percent change in cephalic vein diameter and blood flow** in the middle third of the arm as measured by ultrasonography [Timeframe: from baseline, during Amplifi System treatment (daily), and prior to Amplifi System removal and AVF creation]
- **Mean vein diameter of cephalic vein and blood flow of brachial artery** in the middle third of the forearm as measured by ultrasonography [Timeframe: 1, 2 and 6 weeks post AVF creation]
- **Forearm AVF maturation success at 1, 2, 6 weeks post-AVF creation** [Timeframe: 1, 2, 6-WK post AVF creation]
- **Percentage of subjects who experience an increase in the cephalic vein diameter of  $\geq$ 2.7 mm from their baseline measurement, or an increase of  $>1$  mm from baseline, following treatment with the Amplifi System.** [Timeframe: prior to removal of the Amplifi System and creation of the AVF].

#### Safety Measures

- **Rate of Occurrence of Major Device-Related Adverse Events (MDRAE)\* defined as:** [Timeframe: from device implantation and up to 30 days from device removal and AVF creation]
  - Amplifi System-related death;
  - Amplifi System-related major bleeding, major pneumothorax, major air

## Clinical Protocol FIH-3

Doc No: CLINP1837  
Revision: D  
DCO No: 25-009  
Effective Date: 02/06/25

embolism, major thrombosis, major thromboembolism, major hemolysis, or major thrombocytopenia; local infection

- Amplifi System-related re-hospitalization or prolonged hospitalization;
- Amplifi System-related major surgery or major interventional procedure; or
- any Amplifi System-related complication determined to be an Amplifi System-related major complication by both an Investigator and the Medical Monitor.

\*Detailed definition of Major Device-Related Adverse Events is described in **Attachment 1: Definitions**

- **Rate of Occurrence of Cannulation-related Complications** [Timeframe: from AVF creation through end of follow-up period]

### Exploratory Technical Performance Measures

- **Rate of Occurrence of Amplifi System component replacement** [Timeframe: from device implantation through device removal and AVF creation]
- **Rate of Occurrence of Amplifi System treatment failure** [Timeframe: from device implantation through less than required minimum treatment hours of duration (e.g., 48 hours)]

\*Detailed definition of Treatment Failure is described in **Attachment 1: Definitions**

**Rate of Occurrence of pump stoppages and device malfunction** [Timeframe: from device implantation through device removal]

## 4.6 Inclusion and Exclusion Criteria

### Inclusion Criteria

- Age  $\geq$  18 years
- Indicated for wrist or distal forearm radiocephalic AVF creation based on Investigator's standard practice
- ESRD currently receiving maintenance hemodialysis via a tunneled, cuffed hemodialysis catheter
- Baseline wrist or distal forearm cephalic vein diameter of  $\geq$  1.7 mm and  $\leq$  3.2 mm at the proposed Study AVF creation site, wherein the wrist or forearm cephalic vein at the proposed Study AVF creation site is suitable for Amplifi Distal Outflow Catheter placement and Amplifi System treatment, including:

## Clinical Protocol FIH-3

Doc No: CLINP1837  
Revision: D  
DCO No: 25-009  
Effective Date: 02/06/25

- $\geq 1.7$  mm to  $\leq 3.2$  mm diameter of the wrist or forearm cephalic vein at the proposed Study AVF creation site;
- patency and continuity of blood flow from the proposed Study AVF creation site centrally to the upper arm at the elbow through at least one or more of: 1) the upper arm cephalic vein; 2) the median cubital vein to the upper arm basilic system; or 3) the perforator vein to the deep venous system; and
- no occlusion or stenosis  $\geq 50\%$  along the course of the forearm cephalic vein and at least one upper arm venous outflow up to the subclavian vein, as determined by duplex ultrasonography
- Estimated forearm hemodialysis needle cannulation zone length  $\geq 18$  cm after creation of the proposed Study AVF
- At least one patent internal jugular vein suitable for Amplifi Inflow Catheter insertion
- Subject has voluntarily signed written informed consent

### **Exclusion Criteria**

- 1) Known allergy to Amplifi System components (polyurethane, nitinol), iodinated contrast agents, heparin, or apixaban
- 2) Known or suspected active infection at the proposed time of Amplifi System placement
- 3) Known bleeding diathesis, including from uncorrected coagulopathy
- 4) Known thrombophilia, requiring treatment
- 5) Hb  $<10$  gm/dL
- 6) Platelet level  $< 100,000 /mm^3$
- 7) Need for continued treatment with anti-platelet agents or other anticoagulants (other than apixaban) during the Amplifi System treatment period
- 8) Known history of patent foramen ovale  $\geq 2$  mm
- 9) History of recent intracranial or gastrointestinal bleeding
- 10) Documented recent central venous or right atrial thrombus
- 11) Known presence or recent history of intracranial or gastrointestinal bleeding or presence of underlying conditions that would predispose to intracranial or internal bleeding. Documented recent central venous or right atrial thrombus
- 12) History of recent ipsilateral central venous occlusion, stenosis  $\geq 50\%$ , angioplasty, or stent placement
- 13) Pregnancy, lactation, or plans to become pregnant during the Study

- 14) Unwillingness or inability to comply with procedures specified in the Protocol, or difficulty or inability to return for follow-up visits as specified by the Protocol
- 15) Participation in any other investigational drug or medical device study that has not completed primary endpoint evaluation or clinically interferes with the endpoints from the Study, or planned future participation in such studies prior to the completion of the Study

## **6.0 Study Enrollment, Informed Consent and Subject Withdrawal**

### **6.1 Enrollment**

#### **6.1.1 Informed Consent**

Informed Consent is a process that is initiated prior to an individual agreeing to participate in a study and continuing throughout the individual's study participation. Investigators or designated research staff will obtain a patient's informed consent before any study procedures or data collection are performed.

Patient or Legal Authorized Representative (LAR) will receive a concise and focused presentation of key information about the clinical trial, verbally and with a written consent form. The key information about the study will be organized and presented in lay terminology and language that facilitates an understanding of why one might or might not want to participate. Informed Consent form(s) (ICF) will be EC-approved, and patients will be asked to read and review the consent form. Patient (or LAR) must sign the ICF prior to starting any study procedures being done specifically for this trial. Once signed, a copy of the ICF will be given to the patient for their records. The original form shall be maintained in the patient's medical records at the site. Patient who signed informed can refuse to participate and can withdraw at any time without concern for further treatment.

If new information becomes known to the Sponsor that may affect the risks and benefits of a Subject's participation in the Study, Investigators will revise the informed consent and ICF as necessary and re-consented Subjects. Revisions to the ICF will be approved by Sponsor and ECs prior to re-consenting Subjects. Sites will keep the original signed ICFs for each Subject, including any updated ICFs, on file and available for inspection by Sponsor or its designees.

#### **6.1.2 Enrollment and Study Exit**

After signing informed consent, potential Subjects will be screened against inclusion and exclusion criteria for entry into the Study as close to the scheduled Amplifi System placement time as possible. If all inclusion criteria and no exclusion criteria are met, the patient can be enrolled into the Study as a Subject.

Subjects will undergo screening duplex ultrasonography prior to enrollment and the results will be documented on the appropriate CRF. The protocol for the baseline screening duplex

## Clinical Protocol FIH-3

Doc No: CLINP1837  
Revision: D  
DCO No: 25-009  
Effective Date: 02/06/25

ultrasonography is summarized in the **FIH3 Duplex Ultrasonography Protocol**. A complete blood count (CBC) will be evaluated at baseline and will be used to assess eligibility for the study.

**A patient is considered enrolled in the Study (and a Subject) after all the following criteria are met:**

- patient has provided informed consent;
- Investigator has determined that the patient continues to meet all the inclusion criteria and none of the exclusion criteria; and
- an attempt has been made to treat the patient with the Amplifi System by inserting at least a portion of the Inflow Catheter or Distal Outflow Catheter into the patient's body.

Each subject enrolled in the study will be assigned a unique identification number (see **Section 11.5**). Subjects who receive any amount of Amplifi System treatment and had AVF creation will be followed at 1,2 and 6 weeks after Study AVF creation and will then exit the Study. Subjects who receive any amount of Amplifi System treatment but did not have AVF creation will be followed up to 30 days after Amplifi System removal. Patients in which no portion of the Inflow Catheter or Distal Outflow Catheter was inserted into the body will be considered screening failures and will not be considered enrolled as Subjects. There will be no data entry or follow-up for these patients.

For all consented patients, adverse events shall be collected, and the patient followed until they have resolved, have a stable level of sequelae or, in the Investigator's opinion, are no longer clinically relevant, or study exit (whichever comes first) for safety.

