## Clinical Protocol FIH-3

Doc No: CLINP1837  
Revision: D  
DCO No: 25-009  
Effective Date: 02/06/25

B-Mode Ultrasonography During Amplifi System Treatment (by Investigator)		X	X 		
Contrast Venography (by Investigator)		X	X 	X	
Concomitant Medications		X	X	X	X
Adverse Event Logging		X	X	X	X
Determination of Study AVF Maturation (Y/N)					X
Documentation of unplanned stoppages, malfunction and deficiencies		X	X	X	
Documentation of Study AVF Thrombosis Events, Interventional Procedures, and Surgeries					X
Documentation of Access-Related Thrombosis Events, Interventional Procedures, and Surgeries (all types of access)					X

1. For Subjects that experience a prolonged Pump stoppage only
2. ACT measurements during Amplifi System placement and AVF creation per Amplifi System IFU
3. Daily testing

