## **12.0 Adverse Events and Adverse Device Effects**

All Subjects participating in this study will be assessed for adverse events from the point of enrollment through the follow-up period. Assessments will be performed by the site Principal Investigator. An Independent Safety Board shall monitor the overall safe conduct of the study. The ISB will also make recommendations for or against trial continuation, if required. All serious adverse events (see the definition of serious adverse event, below) occurring after the point of

enrollment through study participation must be reported accordingly.

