## **12.1 Definitions**

### **12.1.1 Adverse Events**

An adverse event (AE) is defined as any untoward medical occurrence, unintended disease or injury, or untoward clinical sign or abnormal lab finding in a Subject, regardless of whether the AE was related to the Amplifi System or Study. Stable, chronic, pre-existing conditions will not be categorized as AEs. However, worsening of these conditions occurring during the Study Period may be categorized as AEs.

Investigators will categorize AEs or suspected AEs as unrelated, possibly related, probably related, or definitely related to the Amplifi System using the relational criteria summarized in **Section 12.2 Classification of Adverse Events**.

Investigators will document all AEs and suspected AEs occurring during the Study Period on the appropriate CRF regardless of whether the AE or suspected AE was related to the Amplifi System or Study. Documentation of the AE or suspected AE will include the characterization of the likelihood the AE was related to the Amplifi System.

Investigators will follow all AEs or suspected AEs until they have resolved, have a stable level of sequelae or, in the Investigator's opinion, are no longer clinically relevant.

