### **12.2.3 Serious Adverse Events**

A serious adverse event (SAE) is defined as any untoward medical occurrence, unintended disease or injury, or untoward clinical sign or abnormal lab finding in a Subject, that:

- causes death;
- causes a life-threatening illness or injury;
- results in permanent disability;
- requires the need for hospitalization or prolongs a hospitalization;

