### 12.2.6 Potential Adverse Events and Serious Adverse Events

AEs and SAEs that may occur during the placement, operation, use, or removal of the Amplifi System, or the subsequent creation and use of an AVF made with a vein treated with the Amplifi System have been identified during the Amplifi System risk analysis process, included in the Amplifi System risk analysis documents, and are summarized here:

- death;
- vascular injury;
- bleeding;
- pneumothorax;
- air embolism;
- vascular thrombosis;
- thromboembolism;
- hemolysis;
- anemia;
- thrombocytopenia;
- Inflow Catheter and Distal Outflow Catheter dislodgement;
- Amplifi System component fracture or laceration;
- Inflow Catheter and Distal Outflow Catheter tunnel or skin exit site infection;
- Amplifi System thrombosis;
- Amplifi System component failure or replacement;
- unplanned re-hospitalization or prolonged hospitalization;
- unplanned surgery or interventional procedure;
- AVF bleeding or thrombosis;
- AVF infection;
- ipsilateral vascular access steal syndrome after creation of an AVF;
- AVF aneurysm or pseudoaneurysm formation;
- allergic reaction; and
- drug toxicity.

AEs and SAEs that may occur during the placement, operation, use, or removal of the Amplifi System, or the subsequent creation and use of an AVF made with a vein treated with the Amplifi System may be related to:

- testing required prior to Amplifi System treatment;
- the Amplifi System placement procedure;
- the operation and use of the Amplifi System;
- procedures where the Amplifi System is evaluated, such as venography;
- the Amplifi System removal procedure;
- surgery to create a Study AVF; and

- cannulation of a Study AVF.

AEs and SAEs that may occur during the placement, operation, use, or removal of the Amplifi System, or the subsequent creation and use of an AVF made with a vein treated with the Amplifi System may or may not be related to the Amplifi System, based on the relational criteria summarized in **Section 12.2 Classification of Adverse Events**.

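### Section 6.1.2 contradicts itself on recording adverse events in consented patients with no catheter inserted, and the Subject-only safety rules can lose a harm from an abandoned placement

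*Protocol*

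**What the plan says.** Section 6.1.2 makes a patient a Subject only when three conditions are met: consent, confirmed eligibility, and insertion of at least part of the Inflow Catheter or the Distal Outflow Catheter. Anyone with no part inserted is a screening failure, and for this group: "There will be no data entry or follow-up for these patients". The following paragraph opens: "For all consented patients, adverse events shall be collected". It goes on to require follow-up until the event resolves, stabilizes or is no longer clinically relevant, or until study exit.

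The later safety sections are written around Subjects:

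- Section 12.0 says Subjects "will be assessed for adverse events from the point of enrollment through the follow-up period". For SAEs, those occurring from "enrollment through study participation must be reported accordingly".
- Section 12.1.1 defines an AE by reference to an occurrence, sign or "abnormal lab finding in a Subject, regardless of whether the AE was related to the Amplifi System or Study". Section 12.2.3 limits the SAE definition in the same way ("abnormal lab finding in a Subject, that").
- Section 14.2.3 summarizes safety data for the Subjects.
- In Table 3, the row "Adverse Event Logging" is blank under Screening and starts in the Day 0 placement column.

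Other parts of the protocol recognize risk before insertion. Section 12.2.6 names "testing required prior to Amplifi System treatment" and the placement procedure as sources of AEs and SAEs. Section 8.5.1 requires contrast venography before either catheter goes in. Appendix 1 starts the treatment period at needle access to the internal jugular or cephalic vein.

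**The concern.** Site staff have two instructions for the same patient: enter nothing and do not follow, or collect the AE and follow it. Choosing the second does not settle the matter, because Section 12 then ties the definitions and SAE reporting to a status this patient never reaches, and Section 14.2.3 summarizes only those who do reach it.

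Safety is one of the study's two stated aims, and placement is an invasive step. With at most ten Subjects, a single serious harm at an abandoned placement is something a reader of the safety report would want to see. If it is never entered, no later analysis plan can recover it.

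**Working it through.** The protocol gives no rate or count for this point, so there is no figure to reproduce. The check is a comparison of texts, followed by a rough size.

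**Step 1: order of events, and which rule starts where.**

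1. Informed consent. The AE sentence in 6.1.2 covers this population.
2. Contrast venography before insertion (8.5.1).
3. Needle access, which starts the treatment period (Appendix 1).
4. First portion of a catheter inserted. The patient is now enrolled and a Subject (6.1.2), and AE assessment and SAE reporting begin (12.0).
5. Device implantation. The MDRAE window opens (Synopsis and 4.5).

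**Step 2: two patients with the same harm at step 2 or 3.**

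- *Placement continues.* The patient becomes a Subject at step 4. Table 3 logs AEs on Day 0 and 14.2.3 summarizes Subjects, so the event is likely to be recorded even though 12.0, read literally, starts slightly later.
- *Placement is abandoned.* The patient is a screening failure. The first rule in 6.1.2 excludes data entry and follow-up; the second requires collection and follow-up. Under 12.1.1 and 12.2.3 the event is not, as defined, an AE or SAE. Under 12.0 it falls before the SAE reporting window. Under 14.2.3 it is outside the summary.

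Only the second patient is lost, so the gap covers harm before catheter insertion in a patient whose placement then stops.

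**Step 3: rough size.** Appendix 2 gives pneumothorax rates of 0.1 to 0.2% for central venous catheters inserted into the internal jugular vein, and 0 to 1% in another review. Assume 11 attempts (10 enrolled plus one abandoned; the number abandoned is not in the protocol). The chance of at least one pneumothorax is 1 − (1 − p)^11:

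- p = 0.001: 1 − 0.999^11 = 1.1%
- p = 0.002: 1 − 0.998^11 = 2.2%
- p = 0.01: 1 − 0.99^11 = 10.5%

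For this complication and at these rates, the figures overstate the chance of a lost event. They count any pneumothorax, and a patient whose placement continues is enrolled and counted. Other access or venography harms would add to them; they are not quantified here.

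**The case against.** The best defense is that the AE sentence in 6.1.2 is the more specific one, follows directly and is expressly for safety, so it can be read as an exception to a general rule about scheduled visits. That is a sensible reading of intent. The text does not say it, however: it excludes data entry without qualification, and the study-exit clause limits how long follow-up lasts, not whether the event is entered.

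A second defense is that the protocol uses the word Subject loosely. Sections 6.1.2, 8.1.1 and 8.5.1 apply it to people before enrollment or insertion, so Section 12 may not be meant to exclude anyone. This weakens any claim of deliberate exclusion. But 6.1.2 defines the term explicitly and says screening failures are not Subjects, so the looseness is itself a reason to fix the wording.

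Third, how a listing is laid out and what denominator it uses can be left to the SAP, which is not at hand. That stands. Collection, definitions and reporting windows, however, are set in the protocol.

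Two stronger readings are tempting and are not supported:

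- *The MDRAE rate would be understated.* One could set 0/10 (exact 95% CI 0 to 30.8%) against 1/11 = 9.1% (0.2 to 41.3%). The arithmetic is right, but it assumes a rare event, and a patient with nothing implanted lies outside the MDRAE window. The MDRAE rate would be 0/10 with or without the correction.
- *The protocol gives three conflicting start times for AE recording.* The consent sentence in 6.1.2 names a population, not a start time. Table 3's Day 0 column is the day of insertion and does not clearly conflict with 12.0. The Appendix 1 treatment period is not stated to be an AE-collection window.

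**Conclusion.** The contradiction within 6.1.2 is real, and the Subject-only wording of 12.0, 12.1.1, 12.2.3 and 14.2.3 means that following the consent sentence alone does not carry the event through to SAE reporting or the safety summary. A harm from venography or needle access in a patient whose placement is abandoned may be unrecorded, unreported and unsummarized.

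The consequence is limited to completeness of the safety record. The study is descriptive, so no test or threshold moves, and the MDRAE rate is unaffected. The gap is narrow and the event unlikely; the size in the working rests on the protocol's literature rates and an assumed 11 attempts. The point should be corrected because the remedy is cheap and the lost information could not be recovered.

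A separate, minor point in the same safety definitions: the hemoglobin limb of major bleeding in Appendix 1 covers overt bleeding with a fall of 3 to 5 g/dL, which literally leaves out larger falls. The other limbs (transfusion, intervention, vasoactive agents, fatal bleeding) will catch most such cases.

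**What to change.** 1. In Section 6.1.2, limit the exclusion of data entry and follow-up for screening failures to scheduled study visits and effectiveness data, and state that AEs and SAEs are excepted.
2. Align Section 12.0 and the AE and SAE definitions in 12.1.1 and 12.2.3 with the all-consented-patients rule, so that events from study procedures before catheter insertion (venography, needle access) are recorded, reported and followed. Starting only at needle access would be narrower than the protocol's own rule and would miss venography.
3. In Section 14.2.3, provide a separate listing of such events in non-enrolled patients. Keep enrolled Subjects as the MDRAE denominator; any denominator for the listing can go in the SAP.
4. Separately, reword the hemoglobin limb of the major-bleeding endpoint so that falls above 5 g/dL also count.

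The cost is a few wording changes, an AE form for abandoned attempts and one listing. Items 1 to 3 leave the MDRAE rate as it is. Item 4 could add only a case with a fall above 5 g/dL that met no other bleeding limb.
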